**A4. WHS/HSR&D Collaboration to Accelerate Comprehensive Care Implementation.** WHS has long been funding the applicant HSR&D investigators and their colleagues to conduct evaluation activities of WVs' health conditions and use (e.g., WV Sourcebooks), needs and experiences (e.g., National Survey of WVs), and evaluations of VA WH programs (e.g., telegynecology). In2012, WHS funded the applicant team to conduct a national expert panel to define gender-sensitive comprehensive care to improve its measurement. WHS then worked with us as primary partner for the WH CREATE, a partnered collaborative research initiative funded by VA HSR&D to use research to further accelerate implementation of comprehensive care for WVs. All five CREATE studies launched in early 2013, including a national organizational survey of comprehensive care arrangements based on the panel results, and a 12-VAMC trial of an EBQI approach to tailoring Patient Aligned Care Teams (PACT) to the needs of WVs. The WH CREATE is an integral initiative supported by the VA WH Research Network (WHRN), which the Blueprint for Excellence cited as central to accelerating innovations in VA WH care (Transformational Strategy 7.2.g).

**A5. WHS Main Evaluation Goals**. WHS seeks a partnered evaluation of their rollout of EBQI as a new strategy for improving quality of WH care in consistently low-performing VA facilities. Building on early evidence of EBQI's promise in activating local teams and leadership around WH PACT improvements, WHS asked for technical specifications to enable contracting for EBQI. They then asked us to adapt our WH PACT EBQI evaluation methods—specifically, key stakeholder (KS) interviews, provider/staff surveys, and

analysis of secondary data—to determine the ways in which EBQI may help low-performing VAs improve quality of care. In our WH PACT study, these methods and measures have revealed new information on WVs' needs and experiences, elucidated implementation barriers, and helped identify actionable provider/staff attitudes and knowledge gaps.

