B4a. Key Stakeholders (KS). Semi-structured gualitative interviews will be conducted at baseline for all sites (Aim #1), as well as immediately prior to the EBQI launch of Groups 2 and 3. Interviews will be conducted at all sites at 12 months post-EBQI launch; in Group 1, interviews will also be conducted at 24 months. Sampling Plan: For Aim #1, we will work with the EBQI contractor to identify facility-level KS (e.g., quadrad member, PC director, WH medical director, WVPM, QI/system redesign lead; n~6/facility) and VISN-level KS (e.g., VISN director, VISN Lead WVPM, VISN system redesign lead; n~4/VISN). We will also interview WHS leaders and EBQI contractor personnel to evaluate leadership and implementation processes. We will adapt KS selection based on the QI targets established at initial EBQI site visits (e.g., add a MH director if the QI project targets MH). For Aim #3, we will seek to re-interview the same KS as in Aim #1, but will pursue replacement personnel in the event of turnover and/or position changes over time. Measures: The Aim #1 baseline interview guide (Appendix 3) includes guestions about the structure and delivery of usual care for WVs, barriers and facilitators to achieving delivery of comprehensive WH care, what (if any) improvements are underway in WH and/or for WVs, familiarity with performance metrics, access to metrics by gender, experience with QI, local culture, perceptions of the care environment, and engagement. The Aim #3 12- and 24-month interviews will assess any changes in care for WVs (staffing, structure, etc.), details of completed/in progress QI projects, perspectives on critical components of EBQI, and anticipated sustainability of local improvements and QI methods. Data Collection: Under the supervision of [name] (Co-PI), KS interviews will be conducted by telephone, recorded and professionally transcribed. Transcripts will be reviewed and edited for accuracy.

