**B4b. Organizational Surveys.** We will use key informant organizational surveys at baseline, 12- and 24months among the 24 participating VA facilities, in addition to annual administered WATCH surveys from WHS (Aim #2a). For Year 1 (FY17), we will rely on national organizational survey modules that will be fielded in Quarter 1 (Q1) as part of a WH CREATE study ([name] & [name], Co-PIs, CRE 12-038) (**Appendix 4**). For Years 2 and 3 (FY18-19), we will re-administer the same surveys, adapting selected domains in relation to EBQI targets of participating VAs. Sampling Plan: All 24 participating VA facilities, including modules for PC directors, WH medical directors, MH directors and WV Program Managers (WVPMs). We will use the tailored design method to identify named respondents for each module. Additional key informants (e.g., chief of medicine) may be considered in subsequent waves if local EBQI targets warrant it. *Measures*: We will include measures of *leadership support*, *local resources* (e.g., sufficiency of time, personnel, equipment), practice structure (e.g., WH care model, staff mix, referral arrangements), *service availability*, *care coordination arrangements* (within and outside VA), *ability to engage in QI* (e.g., barriers to QI, data access by gender), *gender-sensitivity of environment* (e.g., privacy), *local challenges* (e.g., provider shortages, hiring difficulties, practice chaos), *facility type* (e.g., size, academic affiliation, urban/rural), and *EBQI activities*. *Data Collection*: We will field surveys through REDCap, a VA-approved web survey vendor.

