B5b. Quantitative Analyses (Aim #2). To assess effectiveness of EBQI implementation on comprehensive care achievement, we will use data from the organizational surveys (§B4b), provider/staff surveys (§B4c) and administrative data on quality and patient experiences (§B4d). Dependent Variables: We will examine multiple outcome measures as dependent variables: 1) multiple individual measures of comprehensive care achievement, including levels of WH service availability (as noted in VHA Handbook 1330.01), integration of and access to gender-specific and MH care, and other related measures that capture different domains of comprehensiveness; 2) gender-sensitive care delivery, including organizational and provider/staff level measures; and 3) quality of care and patient experience measures. For comprehensive care achievement, we will include as dependent variables the individual measures, and we will also examine approaches to creating an aggregated ordinal score of the individual measures. We will prioritize the final set of dependent variables in consultation with WHS. Independent Variables: The primary regressors of interest will be EBQI exposure (i.e., level of implementation) and time. We will examine the potential moderating effects of practice context and provider/staff knowledge/attitudes (e.g., determine EBQI effects in high vs. low leadership support sites). We will use multiple linear or logistic regression to evaluate EBQI effectiveness. Where appropriate we will adjust for covariates, account for clustering of patients by site, and mitigate bias due to non-response or loss to follow-up through the use of enrollment/attrition weights. Covariates used for adjustment will include patient factors (e.g., facility casemix, proportion of WVs seen), provider/staff factors (e.g., DWHP availability, readiness), and organizational factors (e.g., resource sufficiency, facility size). Clustering by site will be accounted for by fitting hierarchical regression models with random intercepts for the sites (e.g., using SAS PROC Mixed). We will evaluate the goodness-of-fit of a given regression model using standard diagnostics (e.g., Mallow's statistic (Cn)). To adjust for potential non-response bias and loss to follow-up over time for the provider/staff survey samples, we will apply enrollment weights using available characteristics of eligible providers/staff and attrition or "inverse probability of inclusion" weights estimated using an appropriately specified logistic regression model. We will use multiple imputation methods to replace missing values among covariates with hot-deck methods used for imputation as needed. We will estimate site-level effects using the hierarchical regression models with random intercepts for sites. While our sample of sites (24) is small for the estimation site-level effects. EBQI trials of fewer sites have noted significant effects.

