#### D. MANAGEMENT PLAN AND TIMELINE

**D1. Management Plan**. The core team ([name], [name], [name], [name], [name], [name], [name]) will meet weekly, with biweekly Aim-specific meetings focused on evaluation sub-aims (e.g., KS interviews). Monthly

WHS calls already underway will continue throughout the PEC's evaluation period, with additional emails and calls arranged to meet Partner information needs and obtain WHS review/input. We will also participate in regular WHS calls with the EBQI contractor (see *Organizational Chart* in **Appendix 7**). Drs. [name] and [name] will attend 1-2 of the initial in-person EBQI meetings and join initial site engagement calls.

**D2. Timeline/Deliverables**. We will deliver written quarterly reports and briefings to WHS throughout the evaluation, consistent with current practices in annual WHS Memoranda of Understanding (MOUs). The FY17 MOU has already been finalized and will be signed before QUERI PEC review but for a reduced scope of work. Deliverables (below) will be appended to the MOU in Quarter 1 (Q1) if the PEC is awarded.

**FY17:** In Q1, we will work with WHS and the EBQI contractor to finalize operational criteria for classifying low-performing VA facilities. We will review the draft KS interview guide (**Appendix 3**) and provider/staff surveys (**Appendix 5**) with WHS, incorporating WHS and other subject matter experts' feedback as requested. WHS has already approved the organizational survey modules for FY17 (**Appendix 4**); these will be fielded in Q1. WHS will launch facility leadership introductions (including notification of evaluation plans), affirming participation, after which we will randomly allocate sites to EBQI (n=8) or waitlisted control (n=16). We will support contractor training in EBQI technical specifications in collaboration with WHS, document training, and develop a template for use in monitoring EBQI procedures used.

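### Organizational survey domains may be adapted to EBQI targets after randomization, with no rule that keeps the FY17 outcome items; the Aim 2 outcome list is also undated

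*Combined protocol and SAP*

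**What the plan says.** Section B4b uses the national organizational survey modules for FY17. For FY18-19 it says "we will re-administer the same surveys, adapting selected domains in relation to EBQI targets of participating VAs". Further key informants "may be considered in subsequent waves if local EBQI targets warrant it". The sampling plan there covers all 24 facilities, and annual WATCH surveys are a second source for Aim 2a.

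The FY17 content was not built around EBQI targets. Section A4 describes the parent study as "a national organizational survey of comprehensive care arrangements based on the panel results", and Section D2 records that "WHS has already approved the organizational survey modules for FY17".

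Section B4a refers to "QI targets established at initial EBQI site visits", and the Specific Aims list agreement on QI targets among the purposes of the EBQI site visits. For the interviews, the Section D2 timeline speaks of targets in Group 1 in FY18 and in Groups 1 and 2 in FY19.

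Section D2 also promises WHS two sets of results that use these surveys. One is organizational change between Years 1 and 2, overall and by EBQI versus waitlist (FY18 Q4). The other is organizational change across all three survey waves (FY19 Q3).

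On outcomes, Section B5b says "We will prioritize the final set of dependent variables in consultation with WHS" and, for comprehensive care, "we will also examine approaches to creating an aggregated ordinal score of the individual measures". It names no primary outcome, and the Section D2 timeline dates neither decision.

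**The concern.** A survey that measures the effect of an intervention should not be reshaped by the intervention. Here the later waves may be edited toward the goals of sites already receiving EBQI, and the text sets no limit on the editing. Two things are at stake.

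- **Meaning.** An effect on an adapted domain shows change in what exposed sites chose to work on. It is not the same as an effect on comprehensive care as measured in FY17.
- **Baseline.** An item that is reworded or replaced has no comparable FY17 value. It cannot enter a Year 1-2 or three-wave change, and it loses precision in an evaluation whose own Section B5b calls 24 sites small for site-level effects.

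A secondary issue is that WHS helps choose the final outcomes and also receives results by exposure group in FY18 Q4, before the FY19 wave and the summative analysis. With no date on the choice, nothing rules out its being made after those results are known.

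**Working it through.** The plan states no power, alpha or effect size for these outcomes, so there is no figure to reproduce. The checks below use its design.

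**1. Who has targets at each wave.** Section B2 gives 8 + 8 + 8 = 24 sites. The survey waves start in Q1 of FY17, FY18 and FY19 (Section D2). Counting a group that launches in the fielding quarter as not yet exposed, the exposed sites number 0, 8 and 16 of 24. In FY18 the targets come from Group 1, and possibly from Group 2 if its visits precede fielding. Group 3 has had no EBQI visit.

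**2. One common form at all 24 sites.** In a layout with site effects, wave effects and an EBQI indicator, an equal shift from new items in waves 2 and 3 is absorbed by the wave effects. With no true effect and shifts of 0.1, 0.2 or 0.5, the estimated EBQI effect is 0 each time.

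**3. Adapted items at exposed sites only.** The item-version column then equals the EBQI column. The design matrix has 28 columns (24 sites, 2 waves, EBQI, item version) and rank 27. The same shifts return as EBQI effects of 0.1, 0.2 and 0.5. Site fixed effects were used for this check. With the planned random intercepts the two columns are still identical.

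**4. Cost of losing the FY17 value.** The model form is that of Section B5b, "hierarchical regression models with random intercepts for the sites", with wave effects added and total SD set to 1. The within-site correlation r is an assumption. The standard error (SE) comes from generalized least squares, as the square root of the EBQI element of (ΣXᵀV⁻¹X)⁻¹, with V having 1 on the diagonal and r elsewhere.

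| r | SE, three waves | SE, FY18 and FY19 only | Ratio | Equivalent sites, 24/ratio² |
|---|---|---|---|---|
| 0.3 | 0.302 | 0.317 | 1.05 | 21.8 |
| 0.5 | 0.274 | 0.306 | 1.12 | 19.2 |
| 0.7 | 0.224 | 0.271 | 1.21 | 16.3 |

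For the FY18 comparison alone, losing adjustment for the FY17 value multiplies the SE by 1/√(1 − r²) = 1.05, 1.15 and 1.40.

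**5. Undated outcome choice, worst case.** Assume no true effect and k candidate outcomes. The best FY18 contrast M is carried forward alone, and its three-wave statistic T is tested one-sided at 2.5%. Then T = cM + √(1 − c²)Z, where Z is standard normal and c, the correlation between the two statistics, is 0.52 to 0.73 under the design above. Outcomes are mutually correlated at 0 or 0.5. P(T > 1.96) is about 6-9% for k = 5, 7-15% for k = 10 and 9-22% for k = 20. The level, the values of k and the selection rule are all assumptions, not content of the plan.

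**The case against.** The case on the other side is substantial.

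- **The text says the same surveys are repeated, and only selected domains adapted.** Adapting may mean adding questions, in which case no baseline is lost. This stands: the figures in step 4 apply only to outcome items that are reworded or replaced.
- **The targets are those of participating VAs, a term that elsewhere covers all 24 sites.** A reader might infer that only exposed sites have targets. That is an inference from the Specific Aims and Sections B4a and D2, and two of these passages concern interview sampling. Group 2 is allocated in FY18 Q1 and Group 3 launches in FY19 Q1, the same quarters as fielding, so either may have targets by then. The asymmetry is clear only for Group 3 in FY18.
- **A reader might infer that the EBQI estimate is biased.** The documents do not support that. All 24 facilities are listed for the survey, and a common form leaves the same-wave comparison unbiased. The exposed-only version is not ruled out, but it is not stated either.
- **Many B4b domains are context or covariates**, such as leadership support, resources and facility type. Adapting these need not touch an Aim 2a outcome. Appendix 4 is not in the supplied text, so the extent cannot be judged.
- **Added informants** matter only if their answers are pooled into core measures, and nothing says they will be.
- **A reader might infer that outcomes will be picked after results are seen.** Section B5b does not describe this. It keeps the individual measures as dependent variables and speaks of prioritizing them. Aim 2 is also framed as progress-focused, so a confirmatory 2.5% test is brought in from outside.

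What remains is that the permission to adapt has no limit, and the promised change reports need stable items.

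**Conclusion.** The concern holds in a limited form. As written, the plan lets the survey measures behind Aim 2a change after randomization toward what exposed sites work on, and no rule retains the FY17 items. On the likelier reading, a common form, the harm is altered meaning and a lost baseline for any replaced outcome item. The SE loss is about 5%, 12% or 21%, like having about 22, 19 or 16 sites instead of 24, under assumed correlations of 0.3, 0.5 and 0.7. On the reading with exposed-only items, the effect on those items could not be identified. The number of items affected is unknown. WATCH, CDW and SHEPs measures are not touched.

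The undated outcome choice is a real but secondary gap. Its false-finding rates of 6-22% are a worst case and should not be used to judge the weight of the survey point. The change is worth making because FY17 wording dropped from a wave cannot be recovered later.

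**What to change.** **Section B4b.** State that every FY17 item used as an Aim 2a outcome is repeated verbatim in FY18 and FY19, answered by the same informant roles at all 24 sites. Put target-specific items in a short add-on module, given identically to all 24 sites and analysed as exploratory. Keep added informants' answers out of the core measures.

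**Section B5b.** Record with WHS, in a dated document, the prioritized Aim 2 outcomes and the composite's items and scoring. Do this before FY18 Q1 fielding, and in any case before the FY18 Q4 report by exposure group.

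**Cost.** One dated decision, a slightly longer survey and less tailoring of the core modules. Section B6c aims to limit respondent burden, so the add-on should be short. Context items that are not outcomes can still be adapted.

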### **B5. Evaluation Analysis Plan**

**B5a.** Qualitative Analyses (Aims #1 and #3). Analysis of KS interviews will initially focus on data reduction to use findings rapidly and iteratively to inform WHS oversight, support EBQI implementation, and prepare deliverables. Specifically, using an approach designed by this component lead ([name]) (§C1), all interviews will be summarized using a template informed by the interview guide topics (Appendix

3). Summaries will be organized into matrices to compare and contrast findings across roles, sites, and levels (e.g., facility, VISN). In our extensive experience, this data reduction approach is sufficient for generating formative feedback reports to sites and presentations to partners and other stakeholders. The approach will also help generate a preliminary codebook, to be used for more in-depth analysis of the KS interviews using ATLAS.ti, a qualitative data analysis software program that allows for fluid "interaction" of data across types and sources. Initially, a top-level codebook will be developed for the baseline interviews based on the semi-structured interview guide. Using a constant comparison analytic approach, this codebook will be elaborated upon based on emergent themes and adjusted as each round of interviews is completed. Interviews will be compared within facility, across facilities, and over time. These approaches and groupings are easily facilitated within ATLAS.ti, which has the capacity to group data in multiple ways and which allows for maximum efficiency in navigating a complex narrative dataset. In baseline transcripts, we will identify commonly shared knowledge about the structure and delivery of WH care, barriers and facilitators to delivering comprehensive care, as well as pre-implementation knowledge of and experience with QI. In 12- and 24-month KS interview data, we will identify factors that facilitated and impeded EBQI and what changes (if any) were observed in WH care delivery and guality. Consistent with our implementation-focused evaluation in the WH-PACT trial, we will explore which EBQI components are of particular value in improving care and examine clinic and provider characteristics associated with varying levels of EBQI effectiveness and achievement of comprehensive care.

B5b. Quantitative Analyses (Aim #2). To assess effectiveness of EBQI implementation on comprehensive care achievement, we will use data from the organizational surveys (§B4b), provider/staff surveys (§B4c) and administrative data on quality and patient experiences (§B4d). Dependent Variables: We will examine multiple outcome measures as dependent variables: 1) multiple individual measures of comprehensive care achievement, including levels of WH service availability (as noted in VHA Handbook 1330.01), integration of and access to gender-specific and MH care, and other related measures that capture different domains of comprehensiveness; 2) gender-sensitive care delivery, including organizational and provider/staff level measures; and 3) quality of care and patient experience measures. For comprehensive care achievement, we will include as dependent variables the individual measures, and we will also examine approaches to creating an aggregated ordinal score of the individual measures. We will prioritize the final set of dependent variables in consultation with WHS. Independent Variables: The primary regressors of interest will be EBQI exposure (i.e., level of implementation) and time. We will examine the potential moderating effects of practice context and provider/staff knowledge/attitudes (e.g., determine EBQI effects in high vs. low leadership support sites). We will use multiple linear or logistic regression to evaluate EBQI effectiveness. Where appropriate we will adjust for covariates, account for clustering of patients by site, and mitigate bias due to non-response or loss to follow-up through the use of enrollment/attrition weights. Covariates used for adjustment will include patient factors (e.g., facility casemix, proportion of WVs seen), provider/staff factors (e.g., DWHP availability, readiness), and organizational factors (e.g., resource sufficiency, facility size). Clustering by site will be accounted for by fitting hierarchical regression models with random intercepts for the sites (e.g., using SAS PROC Mixed). We will evaluate the goodness-of-fit of a given regression model using standard diagnostics (e.g., Mallow's statistic (Cn)). To adjust for potential non-response bias and loss to follow-up over time for the provider/staff survey samples, we will apply enrollment weights using available characteristics of eligible providers/staff and attrition or "inverse probability of inclusion" weights estimated using an appropriately specified logistic regression model. We will use multiple imputation methods to replace missing values among covariates with hot-deck methods used for imputation as needed. We will estimate site-level effects using the hierarchical regression models with random intercepts for sites. While our sample of sites (24) is small for the estimation site-level effects. EBQI trials of fewer sites have noted significant effects.
